Why do we need quickly adjustable AFO stiffness? Improving mobility in the community requires adjustable ankle stiffness. Ankle joint stiffness varies considerably across different speeds and terrains, which suggests the same for optimal AFO stiffness. Unfortunately, commonly prescribed AFOs are unable to easily or quickly vary the joint stiffness; most are not able to vary stiffness at all. The result, at best, is a single AFO stiffness that is only optimized for ambulating in a single condition at a single speed. AFOs are typically too stiff for slower speeds, often even prevent children from getting off the ground, and yet also unsuitable for stair climbing, ramp ascent or descent, and running. Research has demonstrated that individually tuned stiffness is critical for maximizing improvements in walking performance in CP [19]. There is a need to create an AFO where children can change the stiffness themselves “on the fly.”

Why do we need differential AFO stiffness? There may be long-term danger of locking the ankle and preventing plantarflexion during walking [20]. AFOs typically resist ankle plantar flexion by the same amount that they resist ankle dorsiflexion, resulting in a dramatic reduction in active neuromuscular engagement of the plantar flexor muscles, reduced range of motion, and minimal ankle push-off power [20]. One paper demonstrated that spring like differential stiffness preserves ankle power and work in CP, whereas a rigid configuration did not [18]. There is a need to create an AFO that allows users to maintain some ability to plantarflex at the ankle.

Project Narrative for Prospective Research

Why do we need a modular design? A design that allows the calf cuffs and footplates to be customized and interchanged based on changing needs or growth has several benefits. First, it reduces waste for expensive and hard to recycle composite materials (e.g., carbon fiber). Second, it reduces the need for custom molding sessions. Third, it may allow us to reduce fabrication costs by benefiting from economies of scale when manufacturing common sizes and form factors. There is a need to create an AFO that grows with the child and adapts to their needs.

Purpose:

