Our long-term goal is to establish effective therapies that restore function and improve mobility to enable increased levels of habitual physical activity for improved quality of life and longitudinal health outcomes in individuals with CP. The primary goal of this study is to validate the benefits of, and customer need for, differential and adjustable stiffness AFO features.

Our first aim is to confirm that the differential and adjustable stiffness (DAS) AFO improves plantarflexor push-off power and range of motion compared to standard (physician prescribed) AFOs during walking in CP.

Our second aim is to confirm that the differential and adjustable stiffness (DAS) AFO improves plantarflexor muscle activity while maintaining improved posture compared to standard AFOs during walking in CP.

Our third aim is to validate the need and usability of real-time stiffness adjustment during play and school activities; obtain feedback from the children, their parents, and orthotists to design the MVP.

Lay Summary:

This study seeks to determine how an adjustable stiffness ankle braces affects walking performance and biomechanics in cerebral palsy.

Resources:

This study will take place in the Biomechatronics Lab led by PI Assoc. [name]. Post-docs, graduate student researchers and undergraduate student researchers will be assisting with data collection and processing.

Population & Recruitment

- Maximum number of participants to be enrolled in the study: 11
- Please check all the categories of participants that will be included in the research:

 Children (1-17 yrs old)- Complete Appendix A	 Adults
 Prisoners- Complete Appendix C	 Refugees
 Native Americans - See the Tribal Consultation Policy	 NAU Staff/Faculty
 Pregnant Woman/ Neonates – Complete Appendix B	 NAU Students
 Cognitively Impaired Subjects	 Other- Explain Below

Project Narrative for Prospective Research

- What are the inclusion and exclusion criteria for study participation?

Inclusion Criteria:

- Age between 8-45 years old, inclusive
- Diagnosis of cerebral palsy (CP)
- Gross motor functional classification score level I, II, or III
- Physician-prescribed AFOs of common design (i.e., rigid molded thermoplastic)

Exclusion Criteria:

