Overview: We have developed a differential and adjustable stiffness AFO (DAS-AFO): Differential stiffnesses allows for customizing the stiffness in the plantarflexor and dorsal directions separately to maximize neuromuscular engagement and positive biological ankle power during push-off; A “real-time” stiffness adjusting slider allows for rapid and easy adjustment for different ambulatory conditions (e.g., walking, stairs, running). The primary goal of this study is to validate the benefits of, and need for, differential and adjustable stiffness AFO features. Our first aim is to confirm that the differential and adjustable stiffness AFO improves plantarflexor push-off power and range of motion compared to standard (physician prescribed) AFOs during walking in cerebral palsy (CP). Our second aim is to confirm that the differential and adjustable stiffness AFO improves plantarflexor muscle activity while maintaining improved posture compared to standard AFOs during walking in CP. Our third aim is to validate the need and usability for real-time stiffness adjustment during play and school activities; obtain feedback from the children and their parents.

Experimental Protocol for Aim 1 and 2: Participants will complete two 30-minute practice sessions, and a final assessment. On the final assessment, participants will walk on an instrumented treadmill for 6 minutes with their normal AFOs and with the DAS-AFO tuned to provide just enough dorsiflexor assistance to address drop foot (if present). Testing order will be block randomized. Treadmill speed will be set to each participant’s preference, as will the stance phase plantarflexor stiffness for the DAS-AFO.

Experimental Protocol for Aim 3: Participants will complete a series of play and school activities using the DAS-AFO and their normal AFOs; order will be block randomized. During the DAS-AFO condition, participants will be instructed to adjust stiffness using the simple slider as desired. Activities will include a series of floor-seated, chair-seated, standing, walking, and running (if applicable) tasks to capture the breadth of possible movements encountered during a typical school day. We will use video recording to observe and characterize interactions. These sessions will be followed by dedicated discussion time and validated product evaluation/usability questionnaires.

Outcome Measures: The following experimental data may be collected under each experimental protocol:

- Electromyography

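### The Aim 1 and 2 walks compare the whole DAS-AFO with a rigid prescribed AFO, so they cannot credit differential stiffness as a feature, which the stated primary goal requires

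*Protocol*

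**What the plan says.** **Goal.** The Protocol gives the primary goal under Purpose and again in the Overview (Data Collection Procedures, item 2): "The primary goal of this study is to validate the benefits of, and need for, differential and adjustable stiffness AFO features". It names two features, differential stiffness and adjustable stiffness.

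**Aims 1 and 2.** These are worded at device level. Aim 1 asks whether the DAS-AFO "improves plantarflexor push-off power and range of motion compared to standard (physician prescribed) AFOs during walking in cerebral palsy (CP"). Aim 2 asks whether it "improves plantarflexor muscle activity while maintaining improved posture compared to standard AFOs during walking in CP".

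**Treadmill conditions.** Under Experimental Protocol for Aim 1 and 2, "participants will walk on an instrumented treadmill for 6 minutes with their normal AFOs and with the DAS-AFO tuned to provide just enough dorsiflexor assistance". The same paragraph adds: "Treadmill speed will be set to each participant’s preference, as will the stance phase plantarflexor stiffness for the DAS-AFO". It describes no study setting of the normal AFO.

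**Comparator.** The inclusion criteria require "Physician-prescribed AFOs of common design (i.e., rigid molded thermoplastic"). The Background adds that "commonly prescribed AFOs are unable to easily or quickly vary the joint stiffness; most are not able to vary stiffness at all".

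**Other routes to benefit.** The Background section on quickly adjustable stiffness says: "Research has demonstrated that individually tuned stiffness is critical for maximizing improvements in walking performance in CP [19]. The section on differential stiffness cites a study in which a spring-like differential brace preserved ankle power and a rigid configuration did not. The Background also describes posterior leaf spring AFOs, which return energy and can be made to a custom, though fixed, stiffness.

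**SAP.** The final paragraph tests the adjustable stiffness AFO against shod walking. It does not name the standard AFO as a comparator. It also provides for a sphericity test and a Sidak adjustment, without listing the conditions or the number of comparisons.

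**The concern.** A claim that a feature works needs a comparison in which that feature changes and the rest does not. Here, moving from the prescribed AFO to the DAS-AFO changes several things together, and the Protocol's own Background gives reasons to expect benefit from more than one of them.

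If push-off power or soleus activity improves, the natural reading, given the stated goal, is that differential stiffness has been validated. The same improvement could come from replacing a rigid brace with a more compliant one set for the individual. The choice matters in practice: the Background argues separately for differential stiffness as a design need, and Aim 3 under Purpose feeds the design of the MVP. A wrong attribution could affect which feature is built.

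**Working it through.** The documents give no effect size, standard deviation or power, so there is no figure of the plan's to reproduce. The check is whether the planned conditions can separate the effects.

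**Step 1. How the two treadmill conditions differ**

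| Property | Normal AFO | DAS-AFO | Source |
|---|---|---|---|
| Directional resistance | Typically the same in both directions | Set separately by direction | Background; Overview |
| Overall compliance | Rigid | Spring-based | Inclusion Criteria; Figure 1 caption |
| Individual setting in the study | None described | Drop-foot assistance and preferred stance stiffness | Experimental Protocol for Aim 1 and 2 |

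**Step 2. What the contrast estimates**

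Let D be the effect of differential stiffness and T the combined effect of greater compliance and individual setting. Take them as additive, which is the case most favourable to separating them.

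- Normal AFO: mean = μ
- DAS-AFO: mean = μ + T + D
- Difference: T + D

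The design matrix, with columns μ, T and D, has rows (1, 0, 0) and (1, 1, 1). Its rank is 2 for 3 parameters. Only the sum T + D can be estimated, at any sample size. Splitting T into compliance and setting adds another unknown and no further equation.

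**Step 3. Does another planned comparison help?**

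- *Shod walking (SAP).* This condition has no brace and so needs its own parameter. The rows become (1, 0, 0, 0), (1, 1, 1, 0) and (1, 0, 0, 1): rank 3 for 4 parameters. T and D still enter only as a sum.
- *Aim 3.* The activities again use the DAS-AFO and the normal AFO, with the slider available. That bears on use of real-time adjustment, but no condition separates directional resistance from the rest.

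**Step 4. Illustration under assumed effects**

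Suppose D = 0 and T gives a standardised paired effect dz (mean difference divided by the SD of the differences). The power of a two-sided paired t-test with the maximum n = 11 comes from the noncentral t distribution with 10 degrees of freedom and noncentrality dz × √11. Two-sided testing and every dz below are assumptions. Sidak alpha for m comparisons is 1 − 0.95^(1/m): 0.0253 for m = 2 and 0.0127 for m = 4.

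| Assumed dz | Noncentrality | Power, alpha 0.05 | Power, Sidak m = 2 | Power, Sidak m = 4 |
|---|---|---|---|---|
| 0.5 | 1.66 | 32% | 22% | 14% |
| 0.8 | 2.65 | 67% | 53% | 40% |
| 1.0 | 3.32 | 85% | 74% | 62% |

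This is power for the device-level contrast in the Protocol, which is not the contrast the SAP states. It shows only that a significant device difference is compatible with no effect of the differential feature.

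**The case against.** **The aims are answerable.** Aims 1 and 2 compare the device with the standard AFO, and the two-condition design does exactly that. The Background describes solid AFOs as the type most often prescribed in CP, so a usual-care comparator is reasonable for a study of at most 11 people. This stands. A reader might infer that the trial cannot answer its aims; the documents do not support that. The gap lies between the aims and the feature-level goal.

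**The goal also covers adjustability.** The individual setting exists because the device is adjustable, so it is partly what is being validated, and lower resistance to plantarflexion is itself part of the differential idea. This stands in part: counting three fully distinct factors would be too neat. But Step 2 needs only two effects, and the separate case for differential stiffness remains unidentified.

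**The comparator should not be called untuned.** Correct. The documents do not say how the prescribed AFOs were fitted. They describe setting within the study for the DAS-AFO only.

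**Nothing shows that any softer brace would do as well.** Also correct. The documents make such a brace a possible explanation and no more.

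**The percentages are not false-positive rates.** Correct. If T is not zero, the device-level null is false and rejecting it is right. Setting the figures against a nominal 5% would mislead, and no passage makes one significant test the criterion for validating a feature.

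**Conclusion.** The concern holds in a limited form. The Protocol's treadmill contrast can support a statement about the individually set DAS-AFO as a whole against the prescribed rigid AFO. It cannot support a separate statement about differential stiffness, and neither the SAP's shod condition nor Aim 3 supplies what is missing.

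The gap is structural: one contrast for two or more effects, whatever the sample size. It rests on the conditions as written and on the Background's own account that individual tuning and avoiding a rigid configuration can matter. It does not rest on the illustrative power figures, which depend wholly on assumed effects.

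A reader might also infer that the design needs another treadmill condition to be acceptable. The documents do not support requiring one. They do not show that the prototype can give equal resistance in both directions at each participant's chosen value. Practice and fatigue for a further configuration are not provided for. With 11 participants, the effect detectable with 80% power would rise from dz = 0.94 for one comparison to 1.07 for two with Sidak adjustment. Recruitment was planned to end on 1/1/2025, and the SAP, dated December 18, 2024, already describes data collection in the past tense.

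**What to change.** 1. In the Protocol (Purpose, and the Overview in Data Collection Procedures, item 2) and in the SAP, state that the Aim 1 and 2 contrast estimates the effect of the individually set DAS-AFO as a whole against the prescribed rigid AFO.
2. In the same places, state that no separate benefit of differential stiffness will be concluded from that contrast.
3. Reconcile the comparators: the Protocol names the standard AFO and the SAP names shod walking. The SAP should list the treadmill conditions and say which contrast serves Aims 1 and 2. Until this is done, the statement in item 1 has no matching test in the SAP.

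The cost is wording and a narrower claim. No new procedure, visit or participant is needed, and Aims 1 and 2 keep their present wording.

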- Ground reaction forces
- Motion capture marker trajectories
- Metabolic cost of transport
- Pictorial pediatric exertion scale
- System Usability Scale questionnaire
- Video recordings

Recruitment: We will recruit people from our network of individuals/families of a child with CP and from PT clinics and hospitals across the state of Arizona.

Project Narrative for Prospective Research

Management of Project Personnel: [name] will be responsible for managing project research personnel (graduate students, staff, etc.), including their CITI Training.

3. Please state the estimated time commitment for subject participation: The estimated time commitment to complete the assigned study tasks is 2-3 sessions, each lasting up to 3-4 hours.
4. Does this project involve investigating a Drug, Device or Biologic? No Yes- Complete **Appendix F: Drugs and Devices**
5. Is this project a Clinical Trial? No Yes See [clinical trial guidance](#)
*A research study in which one or more human subjects are prospectively assigned to one or more interventions (which may include placebo or other control) to evaluate the effects of the interventions on biomedical or behavioral health-related outcomes.

Compensation & Costs

(See [Compensation of Subjects](#) Guidance)

1. Provide the amount of compensation (monetary and/or non-monetary) subjects may receive:

Participants will receive \$30 per hour. If participants voluntarily withdraw, they will not receive the compensation. Participants may receive \$10 of travel compensation for every 25 miles traveled to the facility where the study will take place, with a maximum of \$60 per visit. Participants may be reimbursed up to \$120/night of hotel or Airbnb accommodations if an overnight stay is necessary for participation.

2. Describe the process for distribution to subjects, including how the compensation will be prorated, as applicable: Click or tap here to enter text.

Participants will receive a check in the mail at the completion of the study or when requested.

3. Indicate the source of compensation: NIH STTR Grant

 Personal funds	 Funds outlined in the NAU Research Application
---	--

4. Describe any costs, monetary and non-monetary, that subjects may incur:

Extraneous travel expenses to the lab.

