5. Describe the provisions for medical care and available compensation in the event of research related injury, as applicable. If the Human Research has a clinical trial agreement, this language should reflect what is stated in the agreement: None proposed, the activities pose no greater than minimal risk.

Benefits & Risks

Project Narrative for Prospective Research

1. Describe the anticipated benefits of this study to society, academic knowledge or both: [Click or tap here to enter text](#).

This study will advance our knowledge on the design of better ankle braces for children with CP.

2. Describe any benefits that individuals may reasonably expect from participation: [Click or tap here to enter text](#).

There are no anticipated benefits for participants beyond their compensation and perhaps contributing to their personal interest or knowledge in wearable devices.

3. Please describe all physical, psychological, social, legal, and/or economic risks you feel are associated with participation in this research. NOTE: Risks not directly related to the research need not be included in this section: [Click or tap here to enter text](#).

There may be a small risk of physical discomfort due to the device or injury due to falling during walking. We will use a overhead safety tether while participants walk on the treadmill if they appear unstable.

4. Discuss what steps have been taken to minimize risk to subjects/data: [Click or tap here to enter text](#).

We will use a overhead safety tether while participants walk on the treadmill if they appear unstable.

Privacy and Confidentiality

Follow [NAU's data security policy](#). Please make sure to look at the [Data Security guidance](#).

1. What records will the research team be accessing during the research?

Educational Medical Employee Substance Abuse NA

2. What platform is being used to store the data?

 Password Protected Drive	 Encrypted Drive
 External Drive (USB, Flash Drive)	 Departmental Drive
 Cloud Server	 Departmental Office
	 Other- Please explain below

Explain: [Click or tap here to enter text](#).

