3. For each of the platforms checked above (both hard copy and electronic information), discuss the type of data to be stored in each platform (including if the data is identifiable), who may have access to the platform, and how long the information will be stored: [Click or tap here to enter text](#).

De-identifiable experimental data and an excel file with participant demographic information (i.e., walking ability, GMFCS Score, height, weight, age) may be stored on our lab's Google Drive account;

Project Narrative for Prospective Research

this information will be stored indefinitely. Everyone in the Biomechatronics Lab will have access to these data. Identifiable information (e.g., consent form) will be stored in hard copy form in the PI's locked drawer in his locked office; this info will be stored for 5 years after study completion.

4. Discuss how, when and why subjects/data may be removed from the study. If abrupt withdrawal is necessary, discuss how subjects will be withdrawn so that they are not put at increased risk. Discuss what happens if a subject is withdrawn from one part of the study but asked to continue with other parts, such as ongoing follow-up: [Click or tap here to enter text](#).

Withdrawal Circumstances:

Participants will be withdrawn if they are later identified as not meeting the inclusion criteria (e.g., identified as eligible in error), if they miss more than 2-3 research visits in a given experiment, or if they decide to stop participating in the study.

Withdrawal Procedures:

If a participant consents to the study but elects to stop participating after data collection has started, any data that was collected will be retained unless the participant asks otherwise.

Participants must alert the study team in writing of their request to be withdrawn from the study.

Termination Procedures:

Data collected and completed up to the point of withdrawal or termination will still be included in the study unless the participant asks otherwise.

5. Describe steps, if any, to protect the privacy of the subjects throughout their participation in the Human Research (e.g. during the recruitment process, consent process, and/or research procedures): [Click or tap here to enter text](#).

Study team members are trained on appropriate data use and storage, and every reasonable effort is made to minimize risk associated with loss of privacy and confidentiality.

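### Hourly pay is lost entirely on voluntary withdrawal, no proration rule is given, and the withdrawn person's data are used by default

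*Protocol*

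**What the plan says.** Four places in the protocol bear on this.

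- **Compensation & Costs, item 1.** Pay is $30 per hour, followed directly by "If participants voluntarily withdraw, they will not receive the compensation". No exception is made for stopping because of discomfort, instability or a child's wish to stop.
- **Compensation & Costs, item 2.** The form asks for the distribution process, "including how the compensation will be prorated, as applicable". The answer is "Participants will receive a check in the mail at the completion of the study or when requested". It contains no proration rule.
- **Privacy and Confidentiality, item 4.** Under the withdrawal procedures, "any data that was collected will be retained unless the participant asks otherwise". Under the heading on termination, the text adds: "Data collected and completed up to the point of withdrawal or termination will still be included in the study unless the participant asks otherwise". A request to be withdrawn must be made in writing.
- **Benefits & Risks, items 2 to 4.** The risk statement reads "There may be a small risk of physical discomfort due to the device or injury due to falling during walking". The one mitigation given is an overhead tether on the treadmill for anyone who looks unsteady. No personal benefit is expected beyond the pay and perhaps personal interest.

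The inclusion criteria admit participants from age 8, so some will be children enrolled with parental permission and assent.

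**The concern.** Pay builds up by the hour, but entitlement to it depends on not withdrawing. Each completed hour therefore raises the cost of leaving. Pay is also the main tangible return that the protocol offers. For a child, the person who feels the discomfort and the person who weighs the money may not be the same.

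The default on data sharpens the point. The study may use the hours that a withdrawn participant gave while paying nothing for them. The form's own proration question was the place to settle this, and the answer leaves it open.

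What is at stake is the freedom to stop, and fair treatment of those who do. It is not the validity of the comparison between braces.

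**Working it through.** The plan states no total payment, so there is no figure of its own to reproduce. The check has two parts: the scale of the forfeited sum, and a comparison of the passages.

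**Inputs**
- Rate: $30 per hour (Compensation & Costs, item 1).
- Time commitment: "2-3 sessions, each lasting up to 3-4 hours" (Data Collection Procedures, item 3).
- Practice sessions: two, of 30 minutes each, then a final assessment (Experimental Protocol for Aims 1 and 2).

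**Full pay at the stated upper session lengths** = sessions × hours × $30

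| Sessions | Hours each | Full pay | Earned before the last session: (sessions − 1) × hours × $30 |
|---|---|---|---|
| 2 | 3 | $180 | $90 |
| 2 | 4 | $240 | $120 |
| 3 | 3 | $270 | $180 |
| 3 | 4 | $360 | $240 |

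Someone who withdraws just before the last session forfeits $90 to $240. Someone who withdraws near its end forfeits close to $180 to $360. Sessions may be shorter than the stated maximum, so $180 is not a floor.

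**Shorter practice visits (an assumption).** Suppose the two practice visits last only 30 minutes each and the final visit lasts 3 to 4 hours.
- Full pay: (2 × 0.5 + 3) × $30 = $120, up to (2 × 0.5 + 4) × $30 = $150.
- Forfeited after one practice visit: 0.5 × $30 = $15.
- Forfeited after both: 2 × 0.5 × $30 = $30.

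In every case the sum at stake rises with time and is largest during the final visit. For Aims 1 and 2, that is the visit with the treadmill testing.

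**The passages side by side**
- *Item 1 against item 2.* Item 1 says who is not paid; item 2 says when the check goes out. Both can hold. Unresolved is the participant who asks for a check after one session and withdraws before the next: the text does not say whether that money is kept.
- *Item 1 against the withdrawal procedures.* Data are used by default, with an opt-out. Pay is lost whether or not the opt-out is taken.
- *Not covered.* Item 1 names voluntary withdrawal only. The text does not give the pay position of someone withdrawn by the team (for example, for ineligibility or missed visits), nor say whether travel and hotel reimbursement survives withdrawal.

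**The case against.** The strongest reply is that this is a small wording matter on which too much can be built. Several stronger readings are tempting, and the documents do not support them.

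- *That items 1 and 2 contradict each other.* They do not have to. A continuing participant may ask for a check early while one who withdraws is not paid. It is an ambiguity.
- *That the study keeps a withdrawn person's data regardless.* Retention and use are defaults with an opt-out.
- *That anyone who stops loses $180 to $360.* Those are sums for completing the study at upper session lengths. An early stopper loses only what has been earned so far. Multiplying by all 11 participants would assume that everyone withdraws at the very end.
- *That the rule is a demonstrated safety problem or spoils the walking data.* No passage says that resting or ending a walking bout counts as withdrawal, and the written-request requirement suggests a formal exit from the study. The Aims 1 and 2 assessment is 6 minutes per brace at the participant's preferred speed, with the tether available. Nothing in the documents supports an effect on data quality.
- *That the money is already budgeted.* The protocol names the grant as the source but gives no budget total.

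Two further points count against the practical weight. The consent pages are not in the public text, so what participants were told about pay cannot be checked. Recruitment was planned for 1/1/2024 to 1/1/2025, the documents are dated December 18, 2024, and the SAP is in the past tense, so an amendment may reach few future participants.

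All of this stands, but it leaves the core untouched. The forfeiture is a stated rule, the proration question is unanswered, and the tether is mentioned only for the treadmill, not for the standing, walking and running tasks of Aim 3.

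**Conclusion.** The concern holds as a low-cost improvement in participant protection. The protocol pays by the hour, removes all pay on voluntary withdrawal, gives no proration rule, and by default uses the withdrawn person's data.

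The financial penalty for stopping grows with participation. The upper end rests on sessions running to their stated maximum lengths; the lower end on the assumption of 30-minute practice visits. That this may discourage stopping is an inference. It rests on the growing penalty, the inclusion of children, the stated discomfort and fall risks, and the lack of other expected benefit. The documents report no instance of it, and the treadmill tether partly offsets the fall risk.

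The point is minor and does not bear on the statistical analysis.

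**What to change.** Replace the forfeiture sentence in Compensation & Costs, item 1, with: *Participants are paid $30 for each hour completed, including those who withdraw.* Make item 2 agree, so that the proration question is answered and a check sent on request is plainly the participant's to keep. Check that the consent and assent wording matches. Since recruitment may be over or nearly so, apply the rule to anyone who has already withdrawn by paying for the hours they completed.

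It would help to state in the same amendment how pay works when the team withdraws a participant, and whether travel and hotel reimbursement is kept.

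The cost is a short amendment and a small payment for partial participation. For any participant, that payment cannot exceed what completing the study would have cost. Whether the grant has a line for it cannot be read from the documents.
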